6.5 Concomitant Medications

Record all medications taken for treatment of study disease. Please complete a new log line each time a dose is changed.

If a screened and consented subject is started on systemic DMARD, biologic, or systemic glucocorticoids between screening and enrollment then this subject will be considered a screen failure.

6.6 Use of Oral Prednisone

A short course of oral prednisone (\leq 14 days) is allowed in the first month after enrollment or prior to enrollment if local COVID-19 conditions limit availability of intra-articular glucocorticoid injections and total active joint count is \leq 4. Patients treated with a short course (\leq 14 days) will not be considered to have met the primary outcome for systemic medication use. Prednisone dosing should be limited to 20 mg/day.

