6.4 Study Drug Discontinuation Criteria

Study participants who permanently stop study drug in Limit-JIA should be encouraged to continue in the study. If for any reason a study participant must permanently stop study drug, every effort should be made by the Site Investigator/staff to keep the study participant in the Limit-JIA study to collect important safety and clinical data.

Withdrawal from the Limit-JIA study does not automatically withdraw the study participant from the CARRA Registry.

Study participant must be permanently discontinued from the study drug if the following occurs:

- Positive urine pregnancy test
- Non-compliance with study drug. Study participants' compliance with study treatment will be assessed throughout the study. Participants who miss more than one dose should be re-educated on the requirement for treatment compliance. Every effort will be made to keep participants in the study and to re-educate those who continue to miss doses. Participants who continue to be non-compliant after multiple visit assessments may be permanently discontinued from study drug at the discretion of the Site Investigator after consultation with the sponsor.

- Non-compliance with weekly diary. Study participants' must complete their weekly electronic or paper diary between study visits. Participants who are non-compliant after multiple visit assessments may be permanently discontinued from study drug at the discretion of the Site Investigator after consultation with the sponsor.
- Serious Infection
- Physician discretion
- Achievement of any of the primary outcomes as defined in the protocol (disease extension, uveitis and/or need for escalation of systemic therapies)
- SAE attributed to abatacept
- AE attributed to abatacept that at the discretion of the site PI warrants drug discontinuation.
- Conversion to positive PPD or Quantiferon Gold assay result that occurs during the study (if tested as standard of care)

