8 EFFICACY ASSESSMENTS

8.1 Primary Outcome

The primary outcome is the occurrence of any of the following: polyarthritis, active anterior uveitis, or initiation of systemic DMARDs and/or biologics, including systemic glucocorticoids (IV or PO) within 12 months of enrollment.

- (a) Polyarthritis is defined as a cumulative total of ≥ 5 active joints with arthritis since disease onset. The active joint count will be assessed at each study visit from baseline through month 12. Active arthritis is defined as joints with swelling not due to bony enlargement or joints with limitation of motion accompanied by either pain on motion and/or tenderness. For the purposes of counting affected joints, each toe counts as a single joint irrespective of whether it is the proximal interphalangeal joint (PIP), the distal interphalangeal joint (DIP), or both that are affected, consistent with previous clinical trials. Joint counts will be documented using a dedicated case report form (eCRF) at each study visit, tracking both specific joints and number of joints involved.⁶¹
- (b) The presence of active anterior uveitis, defined according to the Standardization of Uveitis Nomenclature for Reporting Clinical Data (SUN criteria) as the presence of one or more cells in each 1mm x 1mm slit beam field (Grade 0.5+, trace cells),⁶² will be assessed at standard of care ophthalmology visits as described by the Heiligenhaus modification of the American Academy of Pediatrics recommendations (see Table 2 in Section 4.3.1). Results will be collected using the existing CARRA Registry uveitis specific eCRF.
- (c) Use of systemic DMARDs and/or biologics, including systemic glucocorticoids (IV or PO) will be captured on the concomitant medication eCRF at each study visit.

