9.2 Primary Analysis

The primary outcome is the proportion of participants experiencing disease extension, (development of polyarthritis or uveitis, or initiation of systemic medications during the 12-month period following enrollment). Participants will undergo evaluations for polyarthritis every 3 months during the 12-month duration of the study. Ophthalmological examinations for uveitis will be performed for enrolled participants according to the schedule in Table 3.

The primary analysis will compare the disease extension rate in the group of patients assigned to receive abatacept in Part II to a weighted average of disease extension rates observed in 6 cohorts (total of 428 patients) from the CARRA Registry who would have met the entry criteria for LIMIT-JIA. [See Appendix: Modification of Study Design and Rationale for Discontinuing Randomization to Control Arm]

The primary analysis will use the logistic regression model, $\log(\pi / (1 - \pi)) = \text{TRT}$, where TRT is the assigned treatment arm (abatacept or control). This analysis will test the null hypothesis that the disease extension rates in the abatacept and control arms are equal. The odds ratio with 95% confidence limits will describe the estimated treatment effect.

A secondary analysis of the disease extension rate will include a stratification factor for Part (I or II) and an interaction term (TRT x PART). This analysis will assess the homogeneity of treatment effect between Part I and Part II. Due to the small number of participants randomized to the control arm, statistical power to detect a TRT x PART interaction is limited.

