9.3 Major Secondary Analyses

Secondary analyses will be done for two study populations. Participants randomized in Part I or assigned to the abatacept arm in Part II will comprise the enrolled population [N approximately equal to 126 (37 Part I, 89 Part II)]. The overall study population [N approximately equal to 554] will include the enrolled population and 428 patients from the CARRA Registry whose disease extension results provided the control mean in Part II.

Secondary analyses for the enrolled population

Secondary analyses will generally be conducted as planned in Part I, although estimation of treatment effects or treatment by factor differences will be imprecise, since more than 80% of participants in the enrolled population are expected to receive abatacept.

Description of the time to disease extension will include cumulative incidence curves for the composite primary outcome and for the components disease extension, uveitis, and initiation of DMARDs or other biologic medication.

Descriptive analyses will summarize participant and caregiver reported outcomes (continuous outcomes of pain interference, fatigue, upper extremity function, mobility, anxiety, depression and global health PROMIS® modules, medication side effects (JAMAR), and the CHAQ). These outcomes will be measured at baseline and follow-up visits as shown in Table 5, and will be analyzed using a mixed model for repeated measures. Preliminary analyses will be performed to identify a parsimonious covariance structure among the repeated measures. The model will include as fixed effects treatment, time, treatment x time interaction, the baseline value of the outcome and the two stratification variables, the risk categories for polyarthritis and uveitis. Time will be treated as a categorical variable. The restricted maximum likelihood (REML) method of estimation and the Kenward-Roger degrees of freedom correction will be used. Contrasts will be constructed among the model parameters to test specific hypotheses. Overall treatment effect will be assessed by testing the null hypothesis of no treatment difference averaged over time. If the treatment x time interaction is significant at $\alpha=0.10$, additional descriptive tests may be done for treatment differences at specific time-points. Since more than 80% of participants in the enrolled population are expected to receive abatacept, there will be limited statistical power to determine treatment effects on these outcomes.

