9.4 Other Planned Analyses

Other planned analyses for the enrolled population

In addition to assessment of treatment differences in PROs, other secondary outcomes include proportion of children achieving clinically inactive disease and/or remission; number of new joints with arthritis; cumulative number of glucocorticoid joint injections; serious adverse events; juvenile arthritis disease activity (JADAS) scores; elapsed time from enrollment to disease extension, uveitis or initiation of DMARD or other biologic treatment.

Sensitivity analyses will be performed to assess the impact of COVID-19 – including measures taken in response to the pandemic such as telehealth visits, missed visits or oral prednisone use on the primary study endpoint. COVID-19 infections will be included in the safety analyses.

Other planned analyses for the overall population

To be described in a separate SAP.

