9.4.2 Power, Sample Size and Type I error

The trial sample size was determined by the intended statistical comparison of the primary outcome (proportion of participants with disease extension) between the abatacept plus usual care and historical care usual care treatment arms [See Appendix: Modification of Study Design and Rationale for Discontinuing Randomization to Control Arm]. It is assumed that the proportion of participants with disease extension will be 34.3% in the usual care arm, and that

this rate will be reduced to 15% in the abatacept plus usual care arm. With 1-sided type 1 error = 0.025, 80 evaluable participants enrolled into the abatacept + usual care arm (compared with the historical control mean from 428 patients) would provide > 95% power using logistic regression. Assuming 10% of participants will not be evaluable, we will enroll up to 89 patients to receive abatacept + usual care arm. See Table 7. Hypothesis testing will be done with the Wald statistic testing the effect of the factor for treatment (abatacept + usual care, vs usual care) in the logistic model with factors for intercept and treatment.

Subgroup or other non-primary analyses may be done by inclusion of additional factors to the logistic regression model.

Table 7: Simulated power for sample sizes in the experimental arm of 10, 20, ..., 80; assuming type I error = 0.025 one-sided.

Sample size (evaluable) in experimental arm N =	Number to enroll assuming a 10% inevaluable rate	Power *
20	23	0.332
30	34	0.591
40	45	0.742
50	56	0.824
60	67	0.900
70	78	0.934
80	89	0.956

* For R_{ex} and R_c = disease extension rates in the experimental and control arms, resp. $H_0: R_{ex} = R_c = 0.343$ (estimated from the historical control group), and $H_1: R_{ex} < 0.15$ (i.e. $< R_c - 0.193$). Power was calculated by simulation of the logistic model, where extension rates followed a binomial distribution [$R_c = 0.343$, $N = 428$] in the control arm, and [$R_{ex} = 0.15$, N (for $N = 20, 30, \dots, 80$ as shown in the table)]. Type I error is 0.025, one-sided.

A sample size of eighty evaluable patients (all enrolled in the abatacept + usual care arm) will provide > 95% power to reject the null hypothesis that the disease extension rate is $\geq 34.3\%$ assuming one-sided type I error ≤ 0.025 and a true disease extension rate in the abatacept + usual care arm $\leq 15\%$. To allow for an inevaluable rate up to 10%, enrollment will be expected to be approximately eighty-nine patients.

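### Section 6.6 exempts short prednisone courses from the primary outcome, Sections 8.1 and 9.2 do not carry the exception, and the available text does not say how the 34.3% Registry rate scored such courses

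*Combined protocol and SAP*

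**What the plan says.** Section 8.1 makes "initiation of systemic DMARDs and/or biologics, including systemic glucocorticoids (IV or PO) within 12 months of enrollment" one of three components of the primary outcome, with no minimum duration. Section 9.2 restates the component as "initiation of systemic medications during the 12-month period following enrollment". The synopsis and Sections 2.1 and 9.1 name systemic glucocorticoids in the same way. None of these places refers to Section 6.6.

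Section 6.6 has two relevant sentences. The first allows an oral course of up to 14 days, before enrollment or in the first month after it, "if local COVID-19 conditions limit availability of intra-articular glucocorticoid injections" and the active joint count is 4 or less. The second says that patients given a short course "will not be considered to have met the primary outcome for systemic medication use". The second sentence repeats the duration limit but not the month, COVID-19 or joint-count conditions.

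The control rate is a weighted average over six Registry cohorts, 428 patients in all (9.2), taken as 34.3% (9.4.2). Both sections refer to an Appendix on the modified design, which was not in the text available for this review. The Wald test is made "in the logistic model with factors for intercept and treatment".

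Section 9.4 plans sensitivity analyses of COVID-19, including "measures taken in response to the pandemic such as telehealth visits, missed visits or oral prednisone use on the primary study endpoint". They are listed for the enrolled population, which 9.3 defines without the Registry: "Participants randomized in Part I or assigned to the abatacept arm in Part II will comprise the enrolled population". Other analyses of the overall population are left to a separate SAP.

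On eligibility, 3.3 (criterion 7) and 6.6 both allow a short course before enrollment. Sections 4.5 and 6.5 make any systemic glucocorticoid started between screening and enrollment a screen failure.

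**The concern.** A child given ten days of prednisone in week 2 under the 6.6 conditions is a primary event by the wording of 8.1 and not one by 6.6. The same course in month 8 could be scored either way, depending on whether the second sentence of 6.6 inherits the conditions of the first.

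In a randomised comparison one loosely worded rule would apply to both arms. Here the two groups come from different data sources, and the primary model has no covariates. If the Registry rate counts short courses and the trial does not, the abatacept rate is lower by the share of children whose only event is such a course, with no drug effect behind the difference. The planned prednisone sensitivity analysis does not reach this comparison. Section 9.5.4 plans efficacy looks from n = 32, so the rule has to be fixed before then.

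**Working it through.** **Inputs.** From 9.4.2: 80 evaluable abatacept patients, 428 controls, control rate 0.343, abatacept rate 0.15, one-sided 0.025, Wald test in a logistic model. From the synopsis: 12 months is 48 weeks, so 336 days. Assumed: d, the share of children whose *only* event is an exempted short course. The documents do not give it.

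**Step 1. Reproduce the stated power.** With x events of 80 and y of 428, z = [log(x/(80−x)) − log(y/(428−y))] / √(1/x + 1/(80−x) + 1/y + 1/(428−y)), and the test rejects when z < −1.96. Summing the two binomial distributions exactly gives power 0.958 at 15% versus 34.3% (Table 7: 0.956). With both rates at 34.3%, the one-sided error is 0.0222. Interim looks are not modelled, because their boundaries are not given.

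**Step 2. Mismatched scoring, no drug effect.** Controls are scored by 8.1 (rate 0.343) and trial participants by 6.6 (rate 0.343 − d).

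| d | Trial rate | One-sided error |
|---|---|---|
| 0 | 0.343 | 2.2% |
| 0.3% | 0.340 | 2.5% |
| 0.5% | 0.338 | 2.7% |
| 0.7% | 0.336 | 2.9% |
| 1% | 0.333 | 3.3% |
| 2% | 0.323 | 4.7% |

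**Step 3. How large can d be on the first-month reading?** At a constant hazard giving 34.3% over 336 days, the risk of any first event by day t is 1 − 0.657^(t/336): 3.44% at 28 days and 3.68% at 30 days. To count in d, a child must also have no later event. That chance is 0.657^((336−t)/336), or 0.680 and 0.682.

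- Cap on d: 0.0344 × 0.680 = 2.3%, and 0.0368 × 0.682 = 2.5%. This would need every first-month event to be an exempted course.
- d = 1% needs short courses to be 0.01/0.0251 = 40% to 0.01/0.0234 = 43% of all first-month events.
- d = 2% needs 80 to 85% of them.
- If 1% of children receive such a course, d is about 0.01 × 0.68 = 0.7%.

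**Step 4. Cost of one rule in both sources.** Suppose the exemption applied to controls lowers their rate by 1 point, to 33.3%. Power at 80 evaluable patients is 93.9% if abatacept stays at 15%. It is 95.1% if the same share of events leaves both arms, since abatacept is then 0.15 × (1 − 0.01/0.343) = 14.6%. The largest abatacept count that still rejects moves from 18 of 80 (147 control events, z = −2.06) to 17 of 80 (143 control events, z = −2.13; 18 of 80 gives −1.91).

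**The case against.** **It is only a missing cross-reference.** Section 6.6 names the primary outcome and states an exception to it, and its second sentence most naturally refers to the course just described. This largely stands for the trial side: 6.6 is a specific exception and does not cancel 8.1. It does not say how the Registry rate was scored, and the scope still has to be inferred.

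**The Appendix may already apply the 6.6 rule to controls.** That is possible. There would then be no bias from this source, and only the wording in 8.1 and 9.2 would need attention.

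**The bias could run the other way.** The allowance exists because joint injections may be unavailable, and an injection is usual care, not an event. If the Registry children had normal access to injections, the same child would be a non-event there, and the exemption could restore comparability. Counting every short course as an event would then penalise abatacept, and a rule on duration and timing alone could remove genuine Registry events. This stands; it is why both scorings should be reported.

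**Section 9.4 already plans a prednisone sensitivity analysis.** This is a partial safeguard. As listed, it does not cover the trial-versus-Registry comparison.

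**Stronger readings that the documents do not support.** A reader might infer that the error rate is close to double its nominal value. That needs d near 2%, which is implausible on the first-month reading (Step 3) and becomes relevant only if 6.6 exempts short courses in any month. A reader might also infer that 6.4 gives sites conflicting stopping instructions, since it lists "Achievement of any of the primary outcomes as defined in the protocol". That phrase takes in the whole protocol, including 6.6, so the link adds little.

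**Conclusion.** The endpoint text is inconsistent as written, and the available text does not show that the two sides of the primary comparison are scored alike. If they are not, with controls by 8.1 and trial participants by 6.6, the comparison favours abatacept: one-sided error is about 2.7% at d = 0.5%, 2.9% at 0.7% and 3.3% at 1%, against 2.2% with identical scoring.

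These figures rest on an assumed d, a constant hazard for the cap, a single final analysis, and an Appendix that does not already settle the matter. It is not established that the trial is biased, or in which direction. The sample-size arithmetic is sound. Severity is minor to moderate: the likely inflation is small, but it falls on the primary comparison and is cheap to remove.

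**What to change.** 1. State in 8.1 and 9.2 whether the 6.6 exception applies to the analysis endpoint and with what scope. Use a rule on duration and timing that can be applied to both trial and Registry data, and fix it before the first interim look at n = 32.
2. Confirm from the Appendix, or re-derive, the 34.3% and Table 7 under that rule.
3. Extend the 9.4 prednisone sensitivity analysis to the primary trial-versus-Registry comparison. Score such courses identically in both sources, once as events and once as exempt, and report both results.
4. Reconcile 3.3 and 6.6 with 4.5 and 6.5 on glucocorticoids taken before enrollment. No clinical rule is proposed here.

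The cost is wording in 8.1, 9.2 and 9.4 and, unless the Appendix settles the rule, a Registry re-extraction with steroid start and stop dates. If the control rate falls by 1 point, power is 93.9% or 95.1%, depending on the assumption in Step 4.

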6.7 COVID-19 Guidance

The following strategies will be employed during the clinical trial to optimize participant safety:

- Provide a fact sheet to all screened subjects on the symptoms of COVID-19
- Administer a COVID-19 questionnaire related to exposure history and physical symptoms
- Obtain and document current temperature at screening and throughout study period. If a potential subject has a temperature greater than 100.4, the subject cannot be enrolled into the trial until they have been afebrile for at least 48 hours and had negative COVID-19 testing. Subjects who develop a fever during the trial will be instructed to follow-up with their local provider for consideration of COVID-19 testing.
- The re-start of study drug after COVID-19 infection is at the discretion of the PI, following ACR guidance.
- See Section 4.9 (Immunizations) and Section 6.4.2 (Temporary Discontinuation for Study Drug) for additional information on COVID-19 guidance

- The COVID-19 Vaccine Clinical Guidance Summary for Patients with Rheumatic and Musculoskeletal Diseases developed by the ACR COVID-19 Vaccine Clinical Guidance Task Force can be found at the following site:
<https://www.rheumatology.org/Portals/0/Files/COVID-19-Vaccine-Clinical-Guidance-Rheumatic-Diseases-Summary.pdf>

7 ASSESSMENT OF SAFETY

The sponsor has engaged DCRI Safety Surveillance to oversee real-time serious adverse event (SAE) collection, evaluation, and, as applicable, expedited regulatory reporting for this study. A medical monitor will be responsible for evaluating site reported SAEs to confirm protocol specific serious reporting criteria, causality assessment, and expectedness compared to the product label.

7.1 Definition

Only Events of Special Interest (ESIs), serious and non-serious, and SAEs will be collected for this study and reported in the RAVE EDC. COVID-19 and related symptoms that meet the criteria of an SAE will be considered unexpected/unanticipated SAEs and reported in the RAVE EDC.

Disease progression will not be reported as an ESI or SAE but will be reflected in the visit joint exams.

Safety will be assessed following initial informed consent, throughout the study and for 30 days post last study dose and it will be assessed by frequency and incidence of ESIs and SAEs. A data safety monitoring board (DSMB) will be convened to review data and safety information from study participants throughout the study.

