2.2 Secondary Objectives

2.2.1 To evaluate the tolerability of weekly SQ abatacept and compare participant and caregiver reported outcomes between the treatment arm and standard of care as documented in the CARRA Registry.

Hypothesis 2.2.1: Patient-Recorded Outcomes (PROs) will remain stable or show improvement at 6 and 12 months in enrolled patients.

Hypothesis 2.2.2: There will be statistically significant differences in (PROs) between the two treatment strategies that can inform future participants and providers in selecting optimal treatments.

2.2.2 To enhance identification of eligible study participants by leveraging the EHR (at selected US sites only).

We will develop and refine proactive EHR-based processes for identifying study participants with recently diagnosed, limited JIA. Collaborating with PCORnet Accessible Research Commons for Health (ARCH) CDRN study sites, we will incorporate PCORnet Common Data Model (CDM) EHR selection queries to continuously generate screening lists of study-eligible study participants and compare with enrollment rates at non-ARCH sites. As feasible, other sites may assist in further validating such EHR selection queries using conventional EHR-based reports

Hypothesis 2.2.2: Incorporation of EHR-based study participant identification methods into conventional screening processes will improve enrollment rates for recently diagnosed participants with early JIA.

2.2.3 To optimize data completeness by leveraging EHR data (at selected US sites only).

Relevant data elements from the EHR at participating ARCH CDRN sites will be linked and incorporated into the CARRA Registry data warehouse for assessment of missing data domains. Linkages will be performed in ongoing completeness-improvement cycles across participating ARCH CDRN study sites.

Hypothesis 2.2.3: Incorporation of EHR data will provide statistically meaningful improvements in data completeness.

2.2.4 To improve clinical trial recruitment and retention.

We will improve clinical trial recruitment and retention of study subjects early in their disease course by identifying barriers and developing improved resources and processes. The study will focus on the following four domains of interest:

1. Understanding of disease/treatment
2. Trust
3. Perceived value of research
4. Time and logistics

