6.4.4 Study Drug Discontinuation Study Assessments

The site Investigator must make every effort to have the study participant return to the clinic as soon as possible after the participant permanently discontinues study drug to determine if they want to withdraw from the study. If the participant chooses to withdraw from the study every attempt should be made to have all evaluations and procedures as outlined in the Schedule of Events performed. (see Table 2 in Section 4.3.1)

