6.4.5 Withdrawal from Study

There are no pre-determined protocol-specific study withdrawal criteria, however, study participants may choose to withdraw from the study at any time and withdraw their consent from further participation in the study. The Site Investigator must document the reason (if specified by the participant) for the withdrawal of consent. Participants who wish to withdraw from further participation in the study should be encouraged to return to the clinic as soon as possible to complete the M12 End of Study Visit. Every attempt should be made to have all evaluations and procedures as outlined in the Schedule of Events performed. (see Table 2 in Section 4.3.1)

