8.2 Secondary Outcomes

8.2.1 Patient reported outcomes

Patient-reported outcomes (PROs), related to pain, fatigue, functional ability, anxiety, depression, global health, family impact, and other medication side effects will be collected and analyzed. PROMIS® measures will be used for each of the outcomes of interest where available. Caregiver/proxy-report will be obtained for participants able to complete the forms in English or in Spanish, and by self-report for children ≥ 8 years of age. The existing iPAD-based, CARRA Registry electronic PRO system will be utilized.

The following PRO instruments will be used.

- PROMIS® pediatric measures selected by the patient/family partners (pain interference, fatigue, functional ability) that have undergone preliminary validation in JIA.^{64,65}
- PROMIS® pediatric measures of anxiety, depression, and global health.
- Side effects of medications, assessed by the yes/no question 11 in the JAMAR.⁶⁶

Table 5: Description of PROs

Outcome	Measure	Timing	Source
Pain	PROMIS® pediatric pain interference	Every study visit	Parent-proxy or child (if \geq 8 years)
Fatigue	PROMIS® pediatric fatigue; short form	Every study visit	Parent-proxy or child (if \geq 8 years)
Functional Ability	PROMIS® upper extremity function and mobility	Every study visit	Parent-proxy or child (if \geq 8 years)
	CHAQ	Baseline, 6M, 12M	Parent-proxy or child (if \geq 8 years)
Anxiety	PROMIS® pediatric emotional distress – anxiety; short form	Baseline, 6M, 12M	Parent-proxy or child (if \geq 8 years)
Depression	PROMIS® pediatric emotional distress – depression; short form	Baseline, 6M, 12M	Parent-proxy or child (if \geq 8 years)
Global Health	PROMIS® pediatric global health measure (PGH-7)	Every study visit	Parent-proxy or child (if \geq 8 years)
Other medication side effects	JAMAR (Juvenile Arthritis Multidimensional Arthritis Report) question #11	Baseline, 3M, 6M	Parent-proxy or child (if \geq 8 years)

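### Section 6.4 lets a non-serious adverse event end abatacept, but neither section 7.1 nor section 6.4.4 requires that event or the reason for stopping to be recorded, so such stops cannot be reliably counted

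*Combined protocol and SAP*

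**What the plan says.** Secondary objective 2.2.1 begins "To evaluate the tolerability of weekly SQ abatacept" and pairs this with participant- and caregiver-reported outcomes.

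Section 6.4 lists the grounds for permanent discontinuation of study drug. A serious event attributed to abatacept is one. A separate entry is "AE attributed to abatacept that at the discretion of the site PI warrants drug discontinuation".

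Section 7.1 sets the collection rule: "Only Events of Special Interest (ESIs), serious and non-serious, and SAEs will be collected for this study". Of safety it says that "it will be assessed by frequency and incidence of ESIs and SAEs".

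Section 6.4.4 asks the site to bring the child back "as soon as possible after the participant permanently discontinues study drug to determine if they want to withdraw from the study". It asks for the Schedule of Events procedures only if the child then withdraws. Section 6.4.5 says the investigator "must document the reason (if specified by the participant) for the withdrawal of consent".

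The side-effect measure in section 8.2.1 is "Side effects of medications, assessed by the yes/no question 11 in the JAMAR", timed in Table 5 as "Baseline, 3M, 6M". Table 2 adds it at interim visits.

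**The concern.** The stopping criteria and the collection rule do not match. Because section 6.4 lists the lesser adverse event separately from the serious one, the plan itself expects some children to stop for a non-serious event. Under section 7.1, that event is recorded only if it is on the special-interest list.

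The number of participants who stop treatment because of an adverse event is a direct measure of tolerability, particularly for a weekly injection given to children with limited disease. As written, the plan does not define that number, require the data behind it, or report it. A reader of the results could see few serious and special-interest events and not know how many families gave up the injections over lesser reactions. Reasons not recorded when drug is stopped are hard to recover reliably later.

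**Working it through.** The plan gives no figure for this point, so the check is a cross-reading of the protocol.

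1. **Which events fall in the gap.** Section 6.2 names infection, mainly upper respiratory, and injection-site reactions as the most common effects. The section 7.5 list takes injection-site reactions only when severe. It takes infections when treated with intravenous anti-infectives or when tuberculous or opportunistic. The list does include hypersensitivity, hepatic events, leukopenia, neutropenia and thrombocytopenia, whether or not serious. Section 7.6 counts medically significant events as serious. What remains is the non-serious, unlisted event, which includes the milder forms of the effects named as most common.

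2. **Whether the reason for stopping is captured elsewhere.** The diary (section 6.4.1) and the weekly Medication Administration Survey (section 5.3) can show that dosing ceased, but neither is specified to record why. Section 6.4 has nine grounds for stopping, and section 6.4.3 adds the participant's own choice. Pregnancy, a primary-outcome event or a serious event could be inferred from other data. A lesser adverse event could not be told apart from physician discretion, non-compliance or family choice. Section 6.4.5 covers only withdrawal of consent.

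3. **What the side-effect item covers.**
   - *Child stops drug and stays.* Sections 6.4 and 6.4.3 encourage this, so the item is still asked at months 3 and 6. It concerns medications in general, and usual care may include NSAIDs. It is not linked to the decision to stop.
   - *Child stops drug and leaves.* Table 2 footnote 1 and section 6.4.5 send the child to the End of Study visit. JAMAR is absent from that column of Table 2, from the Month 12 list in section 4.8 and from Table 5. A child who leaves before month 3 has only the baseline answer, given before treatment. A child who leaves between months 3 and 6 has nothing after month 3.
   - *Interim visits* include JAMAR, but Table 2 footnote 2 ties them to arthritis, uveitis or serious events. Minor intolerance is not a stated trigger.

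4. **What is reported.** Sections 7.1, 8.2.4 and 9.4 refer to serious or special-interest events. None provides for a count of discontinuations for adverse events.

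5. **Scale, by assumption only.** The documents give no rate of stopping for a non-serious, unlisted event. With 89 enrolled (80 / 0.90 = 88.9, rounded up), assumed rates give:
   - 2%: 0.02 × 89 = 1.8, about 2 children
   - 5%: 0.05 × 89 = 4.5, about 4 children
   - 10%: 0.10 × 89 = 8.9, about 9 children

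   These children would have no required event record. Only those who also leave before their next JAMAR visit would lack the side-effect answer.

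**The case against.** Selective safety collection is defensible for a drug whose profile the protocol calls well established and whose doses are approved for children. The special-interest list already takes in many non-serious intolerance events. Objective 2.2.1 is framed partly in patient-reported outcomes, and PROMIS and CHAQ are collected at the End of Study visit. A child who leaves because of side effects may have that reason documented under section 6.4.5. The diary and weekly survey already largely give the last dose and the doses taken. The eCRF is not among the documents and may contain a reason-for-stopping field.

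Most of this stands, and it narrows the point. It rules out saying that these events never reach the database. The supportable statement is that the protocol does not require them to. It also makes extra last-dose, dose-count or adherence items unnecessary. It does not close the gap. A reason under section 6.4.5 depends on the family offering one and does not apply to a child who stops drug but stays. No patient-reported score identifies why drug was stopped.

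A reader might infer that tolerability misses every child who stops for intolerance. The documents do not support that, because stopping drug is not leaving the study, and those who stay keep their scheduled JAMAR visits. A reader might also infer a material understatement of the reported side-effect rate. That would need assumed stopping rates, with every such child leaving before month 3 and answering yes, and no passage supplies any of these.

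**Conclusion.** The point holds in a limited form. Following the plan as written gives no reliable count of discontinuations for non-serious, unlisted adverse events, although section 6.4 provides for them and tolerability is a stated objective. This applies both to children who stay and to those who leave. The loss of the side-effect item is narrower: it affects children who leave the study before their next JAMAR visit.

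The size of any bias is unknown from the documents and probably small. The plan allows for 10% inevaluable from all causes, about 9 of 89, and early leavers for this one reason should be only a part of that. The conclusion assumes that the protocol text governs what sites record. It would weaken if the eCRF already captured the reason for stopping. The primary endpoint, power and type I error are not affected.

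**What to change.** Make four changes to data collection and reporting, none of which alters a stopping rule:

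- **Section 7.1:** also collect any adverse event, serious or not, that leads to permanent discontinuation of study drug. Use the existing SAE/ESI eCRF, and do not apply the 24-hour reporting rule when the event is non-serious.
- **Section 6.4.4:** record the reason for stopping for every child who permanently stops drug, whether or not the child withdraws.
- **Table 2, section 4.8 and Table 5:** add JAMAR question 11 to the End of Study visit when that visit falls before month 6.
- **Safety summary:** report the number of discontinuations for adverse events.

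The cost is one reason field, an occasional extra event entry, and one existing yes/no question at a visit already required. That is a small amount of extra site data entry.
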